# 1. STUDY OBJECTIVES

# 1.1 **Primary Objective:**

The primary efficacy objective of this study is the comparison between groups of the quantification of actual vs planned tooth movements. Changes in tooth position from pre-treatment baseline to end of treatment results will be measured for both Daytime Aligners (control) and Nighttime Aligners (test).

The safety objective of the study will be the incidence of (device or dental) related AEs associated with the planned investigational treatment, in comparison to the incidence of AEs associated with control treatment.

#### 1.2 Secondary Objectives:

The secondary efficacy objective of this study will be to assess overall dentist and subject satisfaction with the treatment.

Safety will also be assessed through subject questionnaire during and after treatment.

# 2. BACKGROUND AND RATIONALE

#### 2.1 Background:

- 2.1.1 Orthodontic clear aligners have become increasingly popular since the advent by Align Technologies in 1998. The esthetics and comfort of using clear aligners instead of traditional wire and bracket braces have greatly contributed to their adoption for orthodontic treatment around the world. Applying slow, continuous force to a subject's teeth is the premise behind clear aligners being safe and effective at treating malocclusions.
- 2.1.2 The aligner system positions teeth by way of continuous gentle force and this system has been applied to the Daytime Aligners which are indicated for the treatment of tooth malocclusion in subjects with permanent dentition (i.e. second molars). The Daytime Aligners (worn 20-22 hours per day) have been available in the US market since 2019 and were initially cleared by the US FDA under pre-market notification K180346. Recently, design changes to the aligners were subsequently cleared by the US FDA under pre-market notifications K230199.
- 2.1.3 Nighttime Aligners have not been cleared by the US FDA, and the purpose of this clinical study is, in part, to gain valid scientific evidence for device safety and efficacy to support US FDA pre-market clearance for the device system. These aligners are to be worn by the subject continuously for 10-12 hours per day (or night). When worn while sleeping, the therapy complements the circadian rhythm of bone remodeling and metabolism for tooth movement (Qin 2019, Luo 2021).

# 2.2 Rationale:

- 2.2.1 Nighttime Aligners program smaller incremental tooth movements into each aligner tray/stage allowing for activation of biological cascade governing orthodontic tooth movement (Krishnan 2006, Kumasako-Haga 2019), with an added advantage of intermittent force resulting in reduced root resorption (Ozkalavci 2018). Movements of molar teeth and extrusive tooth movements are not eligible in the treatment plans for these aligners.
- 2.2.2 This clinical study is designed to provide Straight Smile (doing business as Byte) and Dentsply Sirona data to support performance, efficacy and safety of wearing Nighttime Aligners for 10-12 continuous hours per day (or night). The expressed movements demonstrated by the Nighttime Aligners (investigational/test group) will be compared to the expressed movements demonstrated by the Daytime Aligners (control group), which are worn for 20-22-hours per day. Both control and investigational groups are for subjects with mild malocclusion.
- 2.2.3 This clinical study involves no more than minimal risk (as defined in 21 CFR 50.3(k) or 56.102(i)) to the subjects. Based on this assessment, the IRB will be asked to make a determination that the clinical study does not pose more than minimal risk to the study subjects (non-significant risk) and thus the clinical study is considered to have abbreviated IDE requirements and does not require FDA approval of the study (21 CFR 8.12.2(b)).
  - This request is made in part by reviewing the recommendations provided by the Office of Good Clinical Practice, Office of Special Medical Programs, Office of the Commissioner Food and Drug US FDA in the document "Information Sheet Guidance for IRBs, Clinical Investigators, and Sponsors: Significant Risk and Non-significant Risk Medical Device Studies".

(https://www.fda.gov/regulatory-information/search-fda-guidance-documents/significant-risk-and-nonsignificant-risk-medical-device-studies)

# 4. STUDY DESIGN

The clinical study is a multi-center, controlled, prospective study enrolling on a convenience basis.

The study period for each study subject shall end when the subject discontinues use of the investigational or control devices (i.e., withdraws from the study or completes aligner treatment under the study time frame).

All study subjects will be provided with removable retainers after completion of aligner therapy.

This study shall be carried out in compliance with FDA regulations and Good Clinical Practices (GCP), including but not limited to the Protection of Human Subjects, Informed Consent, Institutional Review Boards, and the Obligations of Clinical Investigators and Sponsors.

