# 8.5 Subject Information

8.5.1 Subject demographic information including subject ID, age, gender, ethnicity and race will be collected and transferred to the corresponding **eCRF**.

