# 9.3 **Primary Efficacy Endpoint**

The primary effectiveness endpoint is the comparison between the treatment groups of the quantification of actual vs planned tooth movements using weighted Peer Assessment Rating (PAR) index.

• Planned percentage reduction in PAR Score (Planned Improvement of Malocclusion [PIM])

In addition comparison between treatment groups will also be performed for:

- Actual percentage reduction in PAR Score (Actual Improvement of Malocclusion [AIM])
- Percentage of Accuracy of Outcome

Quantification and comparison of expressed and programmed tooth movements will be conducted using to measure orthodontic treatment need and outcome, the built-in weighted PAR analysis tool of 3Shape Ortho System software (K152086).

- 9.3.1 The weighted PAR scores for each Digital Study Model (DSM) would be compared as follows:
  - Planned percentage reduction in PAR Score (Planned Improvement of Malocclusion [PIM]) = PAR Score TS- PAR Score TP / PAR Score TS \* 100
  - Actual percentage reduction in PAR Score (Actual Improvement of Malocclusion [AIM]) = PAR Score TS- PAR Score TF / PAR Score TS \* 100
  - Percentage of Accuracy of Outcome = 100% [(|PIM -AIM|/|AIM|) \*100%]

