#### 12.2 Data Analysis

- 12.2.1 The Sponsor and Investigators are not blinded to the study data during the conduct of the trial, and may at periodic intervals analyze the data to assess study progress.
- 12.2.2 If nothing else is stated, descriptive statistics will be given for each variable in the clinical study and p-values may be complemented by confidence intervals as appropriate. When using the terminology descriptive statistics, it is meant that the number of subjects (N), mean, median, standard deviation (Sd), minimum (Min) and maximum (Max) values will be presented for continuous data and frequencies and percentages for categorical data.

- 12.2.3 All tooth movement data analyses will be performed using 3Shape Ortho System (K152086).
- 12.2.4 Three .stl files from each subject would be used for the analysis:
  - A pre-treatment STL file (TS) would be generated by scanning subject's pre-treatment intraoral scan taken before the start of treatment.
  - A planned or programmed STL (TP) file would be obtained from Archform Orthodontic Software System (K213916) after planned or programmed tooth movements have been made based on the treatment plan finalized by the digital lab and study Investigators.
  - The actual post-treatment STL file (TF) would be generated by scanning subject's post-treatment intraoral scan at the end of treatment.
- 12.2.5 Each STL file would convert into a Digital Study Model within the 3Shape Ortho System software to standardize the analysis.
- 12.2.6 Each DSM would be segmented using the "auto segmentation tool" of the software to demarcate each tooth separately.
- 12.2.7 This would be followed by Peer Assessment Rating (PAR) index to measure orthodontic treatment need and outcome (Richmond, 1992). This would be done using the built-in weighted PAR analysis tool of 3Shape Ortho System software. The PAR index will be performed by an external evaluator.
- 12.2.8 The weightage for each component of the PAR index would be set as: maxillary and mandibular anterior segment alignment x 1; buccal occlusion x 1; overjet x 6; overbite x 2; centerline x 4; following the ABO guidelines. The weighted PAR scores for each DSM would be compared as follows:

The PAR Score values for  $T_S$ ,  $T_P$ , and  $T_F$  will be transferred to the eCRF and the following will be calculated:

- Planned percentage reduction in PAR Score (Planned Improvement of Malocclusion [PIM]) = PAR Score TS- PAR Score TP / PAR Score TS \* 100

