- Actual percentage reduction in PAR Score (Actual Improvement of Malocclusion [AIM]) = PAR Score TS- PAR Score TF / PAR Score TS \* 100
- Percentage of Accuracy of Outcome = 100% [(|PIM AIM|/|AIM|) \*100%]

Statistical analysis comparing the two treatment groups using the Wilcoxon rank sum test will pe performed. A two-sided p-value below

5% will be regarded as statistically significant. The null hypothesis of the study is that there is no difference between the two groups.

- 12.2.9 Additional comparisons between treatment groups may be performed and p-values presented using the Wilcoxon rank sum test. Wilcoxon signed rank test may be used for analysis within treatment groups over time.
- 12.2.10 Calculation of Spearman's rank correlation coefficients will be performed to elucidate the relationships between the accuracy of outcome with treatment duration, number of aligners, subject pain levels, and overall subject and doctor satisfaction for each group.
- 12.2.11 All methods used in this clinical study have been previously published and reviewed (Griffith 2021, Grünheid 2022). All data in this clinical study will be analyzed by an independent contractor to remove bias. Any adjustments or modifications to these methods will be duly documented and reported.

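### The arms are compared only by an unadjusted Wilcoxon test and no readable text gives the assignment rule, so a case-mix difference could hide or create a device difference; one baseline-adjusted comparison should be prespecified.

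*Combined protocol and SAP*

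**What the plan says.** Section 4 describes the design in one sentence: "The clinical study is a multi-center, controlled, prospective study enrolling on a convenience basis". The synopsis adds that there are two arms and a control. Section 4.2 sets 50 subjects per arm, with at least 23 evaluable in each.

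Sections 5.3, 8.1 to 8.3 and 8.7 cover screening, enrollment, schedule and aligner delivery, but not how a subject comes to be in one arm or the other. In sections 5.3.3 and 8.2.4, random generation refers to the subject's identification number. What can be read of the synopsis flowchart shows two arms and no allocation step.

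On the analysis, section 12.2.8 says: "Statistical analysis comparing the two treatment groups using the Wilcoxon rank sum test will pe performed". It names no covariate, stratum or site term. Section 12.2.9 allows further comparisons with the same test.

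The measures are in section 9.3.1: "Planned percentage reduction in PAR Score (Planned Improvement of Malocclusion [PIM]) = PAR Score TS- PAR Score TP / PAR Score TS" and "Actual percentage reduction in PAR Score (Actual Improvement of Malocclusion [AIM]) = PAR Score TS- PAR Score TF / PAR Score TS", each times 100 and evidently with the numerator in brackets. TS, TP and TF are the PAR scores at baseline, as planned and at the end. Percentage of Accuracy of Outcome combines PIM and AIM.

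Four other statements bear on the point:
- Section 2.2.2: "Both control and investigational groups are for subjects with mild malocclusion".
- Section 8.5.1: "Subject demographic information including subject ID, age, gender, ethnicity and race will be collected".
- Section 12.2.2: "descriptive statistics will be given for each variable in the clinical study".
- Section 12.2.1: "The Sponsor and Investigators are not blinded to the study data during the conduct of the trial". The same section lets them analyze the data at intervals.

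**The concern.** A two-sample rank test attributes any systematic difference between the arms to the device. That is justified if assignment is random. If the subject, the dentist or the site decides the arm, baseline severity, age and setting may differ between arms, and the planned test cannot separate these from the effect of wear time.

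The error can go either way. The masking direction matters more here, because the synopsis treats the absence of a significant difference as evidence of efficacy. A true Nighttime deficit offset by a favorable case mix would be reported as success. (Reading non-significance as efficacy is a separate problem, which adjustment does not cure.)

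Expressing improvement as a percentage of TS looks like a baseline adjustment. It is one only under a proportionality assumption that the documents do not examine.

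**Working it through.** **1. The plan's own figure.** Section 12.1.2 gives SD 1, difference 1, two-sided alpha 0.05 and power 0.90. The normal approximation is n = 2 × (1.960 + 1.282)² × 1² / 1² = 21.0, so 22 per arm. The exact two-sample t-test has power 0.8997 at 22 and 0.9125 at 23. The stated 23 is therefore reproduced, as an unadjusted calculation that presumes comparable arms.

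**2. Effect of a baseline imbalance.** The documents give no PAR standard deviation, baseline distribution or baseline-outcome correlation, so these inputs are assumptions: normal outcomes, within-arm SD 1, baseline imbalance 0.5 SD, correlation r of 0.3, 0.5 or 0.7. The bias in the outcome is r × 0.5 = 0.15, 0.25 or 0.35 SD. If it masks a true deficit of 1 SD, the apparent deficit is 0.85, 0.75 or 0.65 SD. Simulated results at 23 per arm (10,000 runs per cell; linear ANCOVA on baseline):

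| r | False rejection, Wilcoxon | False rejection, ANCOVA | Missed 1 SD deficit, Wilcoxon | Missed 1 SD deficit, ANCOVA |
|---|---|---|---|---|
| 0.3 | 7.2% | 5.0% | 1 − 0.781 = 21.9% | 1 − 0.912 = 8.8% |
| 0.5 | 11.8% | 4.8% | 1 − 0.673 = 32.7% | 1 − 0.955 = 4.5% |
| 0.7 | 20.1% | 4.9% | 1 − 0.549 = 45.1% | 1 − 0.994 = 0.6% |

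With a 0.25 SD imbalance, Wilcoxon false rejection is 5.0%, 6.5% and 8.2%. At 50 per arm and 0.5 SD it is 11%, 23% and 40%: a larger sample does not remove bias.

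**3. Dividing by TS.** With 3 PAR points remaining, AIM is (10 − 3)/10 = 70% at TS 10 and (20 − 3)/20 = 85% at TS 20. Treatment left the same residual, but AIM differs by 15 percentage points. In an assumed PAR-scale model (TS mean 15, SD 5; mean residual about 4; Nighttime TS 2.5 points higher; no device difference), Wilcoxon false rejection on AIM at 23 per arm is 5% if the residual is proportional to TS and 12% if it is constant. Rank ANCOVA of AIM on TS stays between 4.6% and 5.4%.

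**4. The proposed model.** Rank ANCOVA with TS and age, 23 per arm, imbalance 0.5 SD:
- r = 0.5, age correlation 0.2: false rejection 5.5% against 11.9% for Wilcoxon; power 93.5% against 66.3%.
- r = 0.3: false rejection 5.4% against 7.8%; power 88.1% against 77.4%.
- No imbalance and uninformative covariates: power 88.5% against 89.2%. Residual degrees of freedom are 46 − 4 = 42.

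**5. If the arms are randomized.** The difference in baseline means has SD √(2/23) = 0.295, so chance imbalance beyond 0.5 SD occurs in about 9% of trials. The Wilcoxon test allows for this and keeps its level. What can be lost is power. In the PAR-scale model with balanced arms and a 2-point deficit, adjustment raises power from 67% to 84% if the residual is constant, and leaves it at 88% if the residual is proportional.

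**6. If arms follow site.** With 15 sites split 8 and 7 and an assumed intraclass correlation of 0.05 to 0.20, false rejection is 6% to 11% at 23 per arm. No site term can remove this.

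**The case against.** The strongest reply is that the assignment rule may be drawn in the flowchart. If it shows randomization, the unadjusted test is valid and adjustment is a matter of efficiency. This stands. A reader might infer from convenience enrollment that the trial is not randomized. The documents do not support that: the convenience wording governs entry to the study, and entry to an arm is simply not described in readable text.

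Second, eligibility narrows case mix. Sections 5.1 and 5.2 limit crowding or spacing to 5 mm and exclude molar, extrusive, elastic, extraction, interproximal-reduction and attachment cases. Section 8.1.7 checks the planned movements against these limits. PAR is scored by an external evaluator. All this reduces the risk but does not balance the arms within the eligible range.

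Third, section 1.1 sets the objective as actual against planned movement, and AIM does not use the plan. This also stands, and the fix adds a plan-referenced analysis.

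Fourth, if subjects or dentists choose the arm, adjusting for TS and age leaves preference and expected wear compliance uncontrolled. That is correct, and it is why the assignment rule must be stated as well.

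A reader might also infer much larger errors. A bias of 0.5 SD in the outcome itself would give 64% missed deficits and 36% false rejection at 23 per arm. That bias needs a baseline imbalance of 0.5/r = 1.67, 1.0 or 0.71 SD at r = 0.3, 0.5 or 0.7, and nothing in the documents points to one. Likewise, the PAR-scale model with a constant residual misses a 2-point deficit 66% of the time under imbalance, but balanced arms already miss 33%. About half of that figure comes from dividing by TS, not from case mix.

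**Conclusion.** The point holds in a conditional form. The plan gives no readable assignment rule, and its only between-arm test ignores baseline. If case mix differs, that test can mislead in either direction; if the arms are randomized, it is valid but can lose power.

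The sizes (false rejection about 7% to 20%, missed deficits about 22% to 45% in the masking direction) rest on an assumed 0.5 SD imbalance, correlations of 0.3 to 0.7, normal outcomes and 23 per arm. The 1 SD difference comes from a section that presents itself as an example. An imbalance the other way would exaggerate a deficit instead. The documents neither show nor exclude any of these values.

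**What to change.** 1. In section 12.2.8, prespecify one adjusted between-arm comparison of one achieved outcome: rank ANCOVA of AIM (ranks of AIM regressed on arm and on the ranks of TS and age). As a supporting analysis, run the same adjusted model on a plan-referenced measure, either Percentage of Accuracy of Outcome or TF with TS and TP as covariates; name one. Keep the unadjusted Wilcoxon test as supporting. Fix all of this before anyone compares outcomes by arm, because the sponsor and investigators are unblinded.

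2. State who or what decides the arm, and when. Tabulate TS, age and site by arm, which section 12.2.2 nearly promises already. If the arms are not randomized, limit the conclusions to a non-randomized comparison. Say that unmeasured differences such as expected compliance remain, and that site effects remain if arms follow site.

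3. Treat the place of PIM as the first-listed primary measure as a separate endpoint question. PIM uses only TS and TP, so adjusting it would say nothing about achieved movement.

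The cost is two covariate degrees of freedom (power about 88.5% against 89.2% if the covariates carry no information) and an amendment with IRB review under sections 10.1.1 and 16.1. No new data are needed, since TS and age are already collected.

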# 4.1 **Population**

This study will seek to enroll subjects who are clinically eligible candidates for aligner therapy as outlined in the inclusion/exclusion criteria and are interested in voluntarily participating in this study. Only subjects with permanent dentition (i.e., all second molars) will be screened for enrollment in the study (this is consistent with the intended use statement for the Daytime Aligners [control]).

The clinical study shall be conducted only in the United States.

# 4.2 Number of Subjects

The study shall prospectively enroll up to 100 subjects (50 per treatment arm) on a convenience basis, with a minimum of 50 eligible subjects per treatment arm. A minimum of 23 fully evaluable, compliant, and viable subjects completing treatment in each study treatment arm is required.

#### 4.3 Study Duration

- 4.3.1 The study, as a whole is expected to run for up to 18 months, inclusive of the enrollment period.
- 4.3.2 The minimum planned orthodontic treatment period per subject will be 2 months.
- 4.3.3 The maximum planned orthodontic treatment period per subject will be 8 months, unless a refinement is required.
- 4.3.4 Study subjects will remain on-study until treatment with the final investigational or control device is complete or if the subject wishes to no longer participate in the study (withdraws consent) or Severe non-compliance to protocol as judged by the Investigator and/or Sponsor causing the subject to be withdrawn from the study.

# 5. SELECTION AND ENROLLMENT OF STUDY SUBJECTS

#### 5.1 Inclusion Criteria

For inclusion in this clinical study subjects must meet all of the following criteria:

- 1. Subject willing to participate in the clinical study and able to understand the content of the clinical study.
- 2. Subject must have permanent dentition (i.e. all second molars).
- 3. Subject must be 12 years of age or older.
- 4. Subject must be able to provide and sign consent for themselves, without requiring consent to be given by a legally authorized representative. Parental consent is also required for all participants who are not of the legal age to provide consent themselves (based on participant state of residence).

- 5. The subject requires correction of teeth without planned extrusive movements on either or both arches.
- 6. The subject has no greater than 5 mm of crowding and/or spacing (based on estimation by Investigator).
- The subject does not require planned correction of molar tooth positions, posterior bite or molar classic relationship corrections. Subjects with Class II or Class III malocclusions requiring posterior bite / class correction are not eligible.
- 8. Subjects without prior orthodontic treatment within the past 18 months.
- 9. Subjects who are periodontally stable.
- 10. Subjects without a known history of plastic allergies.
- 11. Subjects who have not had or do not require tooth extractions in preparation for orthodontic treatment with aligners.
- 12. Subjects with a treatment plan that does not include the use of elastics.

# 5.2 Exclusion Criteria

Any of the following is regarded as a criterion for exclusion from the clinical study:

- 1. Unlikely to be able to comply with clinical study procedures according to Investigator's judgement.
- 2. Unable or unwilling to return for follow-up visits.
- 3. Previous enrolment in the present clinical study.
- 4. Involvement in the planning and conduct of the clinical study (applies to both Sponsor personnel and the clinical study site)
- 5. Participation in another clinical study that may interfere with the present clinical study.
- 6. Subjects who have active carries, where there is no plan to correct them prior to the start of aligner therapy.
- 7. Other dental or clinical pathologies, which in the judgment of the Investigator, deem the candidates inappropriate for participation in the study (e.g. clinically significant periodontal disease or gingivitis, interproximal decay, etc.).
- 8. The subject require interproximal reduction or attachments to obtain a corrected malocclusion.
- 9. In addition to the criteria listed above, this product is contraindicated for use in adult and adolescent subjects presenting with the following dental conditions:
  - Active periodontal disease

**CONFIDENTIAL:** The information in this study protocol is strictly confidential and is available for review to Investigators, study center personnel, the ethics committee, and the health authorities. It will not be disclosed to third parties without written authorization from the Sponsor, except to obtain informed consent from persons receiving the study treatment. Once the protocol is signed, its terms are binding for all parties.

- Severe open bite or severe overjet
- Tooth malocclusion requiring surgical correction
- Subject with mixed dentition
- Subject with a skeletally narrow jaw
- Dental prosthetics/implants or significant number of missing teeth

10. Known pregnancy, pregnancy tests will be performed as per local requirements.

